reporting and to improve the transparency of the data collection and analysis phases of these two studies, we decided to write this statistical analysis plan before any statistical analyses were conducted. The study results will be reported according to The Transparent Reporting of a multivariable prediction model for Individual Prognosis Or Diagnosis (TRIPOD) -statement.³²

Objectives and hypotheses

The objectives of the first study:

- To determine the rate of secondary surgery due to fracture nonunion of AO/OTA type A and C distal femur fractures treated primarily with lateral locking plate
- To evaluate how accurately the previously identified patient- and injury-related risk factors predict a distal femur fracture nonunion

The objective of the second study:

- To evaluate how accurately the previously identified treatment-related risk factors predict a distal femur fracture nonunion
- To evaluate a secondary prediction model combining the treatment-related risk factors and the three most important patient- and injury-related predictive factors from the first study

STUDY METHODS

This study is a retrospective cohort study conducted in level 1 trauma centre at the Helsinki University Hospital with a catchment population of around one million for these fractures. After receiving permission from our institutional review board, we identified all patients with a distal femur fracture treated at our institution between 2009 and 2018 using the electronic patient record system. Both of our future articles regarding the prediction of distal femur fracture nonunion will use the same patient data.

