The detailed inclusion and exclusion criteria are shown in Table 1. We included patients aged 16 years or older with traumatic distal femur fractures. The first surgical procedure had to be performed at our institution in 1 month (≤ 31 days) after trauma. Patients with a stress fracture, a pathological fracture, epicondylar or subchondral fracture, or ligament sprains such as ACL, PCL, MCL or LCL avulsion injuries, were excluded. We included in these studies The AO Foundation/Orthopaedic Trauma Association (AO/OTA) classification 33A- and 33C-type fractures³³ treated with a lateral locking plate. Only distal lateral anatomic locking plates for distal femur were included and any other unconventional plates used in the distal femur were excluded. Those fractures treated with a lateral and medial plate (double plating-method) or with lateral plate and femur nail together were excluded. We excluded patients treated with a retrograde or an antegrade femoral nail, a constrained prosthesis, femoral amputation, non-surgical treatment and patients who died before the final treatment. We excluded the operatively treated unicondylar fractures (AO/OTA classification 33B,) because the fixation methods and principles used for the operative treatment for B-type fractures differ from the A- and C-type fractures.

The first author examined all femur fracture X-rays included in the study. A fracture was classified as a distal femur fracture if a part of the fracture site was located on a metaphyseal

area of distal femur. Metaphyseal area of distal femur was defined with a square-method as proposed by Urs Heim.^{34,35}

We excluded the patients whose follow-up was too short to define the final healing status of the fracture. The patients who had a radiological or clinical union of the fracture site during the follow-up, and the patients who had any surgical intervention to promote the bony union were accepted to this study.

We defined a fracture as nonunited only when a patient had a surgical intervention to promote bony union in the fracture site. In addition, a reoperation done for a plate failure at least 3 months after operation and without a new trauma is assumed in this study to occur because of a nonunion of the fracture.

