The radiological union in the x-ray is defined as a bridging callus consolidation on three out of four cortices of fracture site and vanishing of fracture lines during the follow up. If the radiological follow-up ended before the fracture was radiologically united in x-rays, we followed up the patients from electronic patient records of all medical specialties and general medicine at least 12 months after operation and examined their ambulating status and other problems regarding the fracture site. If there were no clinical signs of problems with distal femur fracture such as pain during gait or pain on the fracture site, and those patients did not come back to our institution after 1 year at least, we assumed that the fracture has been healed and those patients were included in the study. Our institution Helsinki university hospital is the only place in our catchment area where distal femur fractures are treated and based on that we assumed that those patients, who had problems with healing such as non-union or plate failure, will return to the Helsinki university hospital for reoperation.

Surgical treatment

The two different plate types used in this study were DePuy Synthes 4,5mm VA-LCP Curved Condylar Plate (Stainless steel) and DePuy Synthes Less invasive stabilization system (LISS) for LCP-DF-plate (Titanium alloy). The fractures included in this study were operated by the senior orthopaedic trauma surgeons or orthopaedic residents. The plate type, screw types and proximal fixation used in the operation were chosen by the treating surgeon. The methods for proximal fixation were 4.5mm locking- and cortical screws and with peri-implantary fractures also cables and 3.5mm proximal locking attachment plates were used. The fracture fixations were performed both with absolute or relative stabilization techniques according to treating surgeon's preference. There were no proper data available from the surgical records if the operation was performed with a mini-invasive or an open technique. There were not any standardized postoperative protocols for weight-bearing or a cast or an orthosis use. Usually, the non-weight-bearing period was 6-10 weeks after operation. After that patients normally continued with half-weight-bearing, and the weight-bearing as tolerated was allowed from the weeks 10 to 12 depending how the fracture was healed. Typically, the follow-up visits were at 6 and 12 weeks at the outpatient clinic and after that if deemed necessary.

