Table 1. Inclusion and Exclusion criteria used in the study.

Inclusion

- Age > 16 years- AO/OTA type A or C distal femur fracture- Fracture located on the metaphyseal area of the distal femur (square method)- Operative treatment in the Helsinki University Hospital with a distal femur anatomic lateral locking plate- Operative treatment within 1 month after trauma- Operative treatment between years 2009 and 2018
Exclusion

- Stress fracture- Pathological fracture- An epicondylar or subchondral fracture- A ligament sprain in distal femur- Treatment with a double-plating method or with both plate and nail- Non-surgical treatment and patients who died before the treatment- Treatment with an unconventional plate (other than distal femur plate)- Patients whose follow-up criteria not fulfilled

Data collection

The details of the data used in this study are shown in Table 2.

The principles of the injury-related factors are as follows. Distal femur fractures were classified according to the AO/OTA classification system 2007.³³ High energy trauma was defined as a motor-vehicle accident or a fall from a height of >1m. Low-energy trauma was defined as a fall from a height of < 1m such as a fall from the same level or a fall from a chair or a bed. All fractures were classified as open or closed injuries. Open fracture was defined as a fracture with an open wound or break in the skin near the broken bone. The definition for a periprosthetic fracture in this study was a distal femur fracture above a knee prosthesis. Segmentally comminuted fractures were defined as A3, C2 and C3- fractures according to the AO/OTA-classification. The definition for medial fracture comminution was that more than one fracture line reached the medial cortex on the antero-posterior x-ray forming one or more loose bone fragments on the medial side. Fracture zone length was measured from the postoperative x-rays where the fracture was reduced. The known plate length in millimetres was used to correctly calibrate the x-ray.

The principles of the treatment-related factors are as follows.

1. The x-ray was calibrated using the plate length
2. Plate length in millimetres: Measured as the plate shaft holes first and then in millimetres given from the manufacturer
3. Plate working length: Defined as a distance from the nearest proximal screw to the nearest distal screw on each side of the fracture

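### The assumed-healed rule relies on patients returning to the hospital, which the SAP justifies only for its catchment area, but entry to the cohort does not depend on residence.

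*SAP*

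**What the plan says.** All of the following is in the SAP.

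- **Cohort** (Study Methods): "we identified all patients with a distal femur fracture treated at our institution between 2009 and 2018". Table 1 fixes the place of surgery: "Operative treatment in the Helsinki University Hospital with a distal femur anatomic lateral locking plate". Neither the text nor Table 1 mentions place of residence.
- **Event** (Study Methods): "We defined a fracture as nonunited only when a patient had a surgical intervention to promote bony union in the fracture site". A reoperation for plate failure at 3 months or later, without new trauma, also counts.
- **Union on x-ray** (Study Methods, before Surgical treatment): "bridging callus consolidation on three out of four cortices of fracture site and vanishing of fracture lines during the follow up".
- **Union by assumption** (same place): where x-ray follow-up ended earlier, "we followed up the patients from electronic patient records of all medical specialties and general medicine at least 12 months after operation". Two conditions then make the fracture count as healed. The first is an absence of symptoms, worded as "no clinical signs of problems with distal femur fracture such as pain during gait or pain on the fracture site". The second is that the patient stayed away: "those patients did not come back to our institution after 1 year at least, we assumed that the fracture has been healed".
- **Ground for the assumption**: "Our institution Helsinki university hospital is the only place in our catchment area where distal femur fractures are treated". From this the SAP concludes that patients with a nonunion or plate failure would come back for reoperation.
- **Follow-up exclusion** (Study Methods and Table 1): patients whose follow-up does not allow the healing status to be determined are left out. This is not linked to residence or to how far the records reach.

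**The concern.** The argument that a patient with trouble would come back holds for people who live where this hospital is the only provider. It says nothing about someone operated on there who then goes home to another region. That patient leaves no complaint in the local records and does not return, whether the fracture healed or was reoperated elsewhere. Both parts of the assumed-healed rule can then be met simply because information is missing.

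Two things are at stake. The first objective of the first study is the rate of secondary surgery for nonunion, and each reoperation coded as healed lowers that rate directly. The remaining objectives are prediction models on the same outcome. If missed reoperations are spread unevenly over a predictor such as trauma energy or age, its coefficient and the calibration are distorted too. The SAP does not show that residence is related to any predictor, so this second effect is possible but not demonstrated.

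**Working it through.** The SAP states no sample size, event count or share of out-of-area patients, so there is no figure to reproduce. The check sets the passages side by side and adds an illustration.

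**Step 1. Does the justification cover the cohort?** The sole-provider argument is limited to the catchment area. Entry requires an operation at the hospital and nothing about residence. The justification therefore covers only part of the population that the eligibility rules admit.

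**Step 2. Does another rule close the gap?** The follow-up exclusion might, but it does not say whether an empty record, or residence elsewhere, counts as insufficient. The record review spans all specialties and general medicine, but the SAP does not say whether it reaches beyond the region. The gap stays open.

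**Step 3. Could the route be used often?** Typical visits were at 6 and 12 weeks, with later ones only if needed (Surgical treatment). A fracture that did not meet the x-ray criterion on its last film goes to the assumed route. The SAP does not plan to report how many did.

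**Step 4. Effect on the rate (illustration).** Let p be the true rate of reoperated nonunion and s the share of those reoperations done elsewhere and coded healed. The patients stay in the denominator, so

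observed rate = p × (1 − s).

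The SAP's introduction cites rates of 6% (a meta-analysis) and 10–22% (diverse studies). The values of s are assumed.

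| True rate p | s = 0 | s = 5% | s = 10% | s = 20% | s = 30% |
|---|---|---|---|---|---|
| 6% | 6.0% | 5.7% | 5.4% | 4.8% | 4.2% |
| 10% | 10.0% | 9.5% | 9.0% | 8.0% | 7.0% |
| 22% | 22.0% | 20.9% | 19.8% | 17.6% | 15.4% |

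**Step 5. Effect on a predictor (illustration).** Take two groups with the same true rate p but different missed shares s1 and s0. The true odds ratio is 1. The observed one is

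odds[p(1 − s1)] / odds[p(1 − s0)], with odds[x] = x / (1 − x).

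With p = 10% and s0 = 5%:

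- s1 = 10%: (0.09/0.91) / (0.095/0.905) = 0.94
- s1 = 20%: (0.08/0.92) / (0.095/0.905) = 0.83
- s1 = 30%: (0.07/0.93) / (0.095/0.905) = 0.72
- s1 = 40%: (0.06/0.94) / (0.095/0.905) = 0.61

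With s1 = s0 the observed odds ratio stays at 1. This second effect needs the loss to differ between groups.

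**The case against.** The strongest reply is that the rule does not rest on silence alone. Records of all specialties and general medicine were searched for at least 12 months, ambulating status was examined, and patients with inadequate follow-up are excluded. A visitor with no entries after discharge can be read as failing that follow-up requirement. The SAP also does not say that any out-of-area patient was included. Most of this stands: the text does not show that such patients were coded healed. What remains is that the text allows it, because neither the exclusion nor the healed rule says how an empty record or residence elsewhere is handled.

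It is also fair to object that every share used in the illustration is assumed. That is right. The figures show how the bias behaves, not how large it is here, and the range starts at zero.

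A reader might further infer that patients who do not walk are missed events, since gait pain cannot occur in them. The SAP does not support this. Nonunion is defined by surgery, so an un-united fracture that was never reoperated is a non-event by definition, and the secondary-surgery rate is not understated on that account. Gait pain is also only one example of a sign. Fracture-site pain needs no walking, and a reoperation at the hospital is captured whether or not the patient walks.

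**Conclusion.** The point holds for patients living outside the catchment area. The assumption of return is justified for residents only, the cohort is not limited to residents, and the follow-up exclusion does not clearly remove the others. A reoperation elsewhere can therefore enter the data as a healed fracture. The bias on the secondary-surgery rate can only be downward through this route, by the fraction s of reoperations lost. Bias in a predictor arises only if that loss differs across its levels.

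The size cannot be determined from the SAP. It depends on how many out-of-area patients were operated on, how often they were reoperated elsewhere, and whether the reviewed records would show it. If none were included, or the records reach beyond the region, the effect is nil. The correction is worth making before analysis because the SAP leaves this open and the remedy is cheap.

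**What to change.** In Study Methods and Table 1, restrict the analysis set to patients who lived in the catchment area, or whose records demonstrably cover at least 12 months after operation or the time to death. Apply this to events and non-events alike, and class everyone else under the existing exclusion for unmet follow-up criteria. Coverage should be judged on grounds other than the reoperation itself. Otherwise an out-of-area patient who happened to return would qualify because of the outcome.

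Do not add a requirement of documented walking, and do not impose the residence condition on non-events only. Either would select on the outcome, and a walking requirement would also remove frail patients. With an assumed 200 fractures and 20 events, dropping 15 or 40 non-events alone raises the rate from 10% to 20/185 = 10.8% or 20/160 = 12.5%.

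Report how many fractures were classed as healed by x-ray and how many by assumption. As a sensitivity analysis, refit the models with x-ray-confirmed unions plus events. State that this refit overstates the rate, because it drops only non-events.

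The cost is SAP wording, the extraction of residence from the records, and the probable loss of a few patients.

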Additionally, there has been discussion in the recent literature about the stiffness of the plate construction that affects the healing environment and micromotion in the fracture site. A few studies investigated different plate fixation variables as a risk factor for nonunion.^{15,16} The plate material can affect the rigidity of fixation. Stainless steel plates appeared as a risk factor for nonunion compared to titanium plates.^{16,23} There was less callus formed with fractures treated with a stainless steel plate compared with titanium plate.¹⁷ The plate length, the screw selection and the screw placement in the plate can affect the construction rigidity. Constructs with a plate length > 9 holes appeared to fail less likely compared to shorter plates.¹⁵ The plate constructs with all locking screws have been reported to be 2.9 times more likely to develop a nonunion compared to the plate constructs with both locking and nonlocking screws.³⁰ In addition, healed distal femur fractures had more empty plate holes adjacent to fracture site compared to fractures that did not heal.¹⁷ The mini-invasive plate insertion spares the blood circulation to the periosteum. The submuscular plate insertion reduced nonunion rate in distal femur fractures instead of open reduction.^{21,25}

This study explores the predictive value of previously identified explanatory risk factors for a distal femur fracture nonunion and identifies patients who are at risk for distal femur fracture nonunion after lateral locked plating. In a predictive model, there is no need to consider the causality of the individual risk factors which is a common caveat in studies exploring potential risk factors for a given outcome.³¹ This prediction model could be applied into clinical practice to identify and advise patients with known risks before operation and to more carefully follow-up patients with an elevated risk for fracture nonunion.

Our plan is to publish this study in two consecutive articles: the first article examines the patient- and injury- related factors and the second article examines the role of different treatment related factors in the prediction of distal femur fracture nonunion. To avoid selective

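### Fracture zone length, a Study I predictor, is measured on postoperative x-rays, so a Study I model that keeps it cannot be applied as defined before surgery

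*SAP*

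**What the plan says.** At the end of the background (under Risk factors for non-union), the SAP names two possible clinical uses for the prediction model: to "identify and advise patients with known risks before operation and to more carefully follow-up patients with an elevated risk for fracture nonunion". The first use comes before surgery. The second can come after it.

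Under Objectives and hypotheses, the accuracy objective of the first study is "To evaluate how accurately the previously identified patient- and injury-related risk factors predict a distal femur fracture nonunion". It sets no time of prediction.

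Table 2 lists fracture zone length among the injury-related factors of Study I. The Data collection section defines how it was obtained: "Fracture zone length was measured from the postoperative x-rays where the fracture was reduced". It adds: "The known plate length in millimetres was used to correctly calibrate the x-ray".

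Statistical principles plans three models: patient- and injury-related variables (Study I), treatment-related variables, and a combination of the most important variables from each. Before fitting, a redundancy analysis checks collinearity, with data reduction where this seems reasonable, and very skewed binary variables may be excluded. R² is estimated for the fitted models, and a calibration plot is planned for each of the three.

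**The concern.** A prediction model can be used only when all its inputs are known. Fracture zone length, as this SAP defines it, requires a reduced fracture and a plate of known length on the film, so it requires a completed operation. A surgeon who wants to advise a patient beforehand does not have that value and could not enter it into the fitted equation.

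At stake is which model can support the preoperative use. If fracture zone length stays in Study I, the plan contains no model without treatment-related variables that can be applied as defined before surgery. Replacing the missing value by a length read on an unreduced film without a plate would not settle this. The coefficient and the calibration would have been estimated on reduced, plate-scaled films, and the SAP neither defines a preoperative measurement nor plans a comparison of the two.

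**Working it through.** The SAP gives no figure on this point, so there is none to reproduce. The check sets the relevant statements side by side.

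1. **Time of use.** The background names two uses, one before operation and one in follow-up.
2. **Which model could serve the first use.** Of the three planned models, the second consists of treatment-related variables and the third includes some of them. Table 2 shows these to be plate and screw features, such as working length, empty holes and proximal cortices, recorded from the fixation as performed. That leaves Study I.
3. **What Study I contains.** Table 2 gives 5 patient-related and 7 injury-related factors: 5 + 7 = 12 candidates. Fracture zone length is one of the 7.
4. **When that candidate is known.** Data collection states a postoperative source, with the fracture reduced and the film scaled by the plate. It is the only one of the 12 for which a postoperative source is stated.
5. **Whether the plan would remove it.** Statistical principles offers two routes.
   - Redundancy analysis with data reduction addresses collinearity, not availability.
   - Exclusion of very skewed binary variables cannot apply, because fracture zone length is a measured length.

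   The variable may therefore drop out or stay, and if it drops out, the reason will not be its timing. Retention is plausible. The background cites one study that linked longer comminution to plate failure, although another found no correlation between length of comminution and nonunion.
6. **Consequence if it stays.** One input of the Study I equation is unavailable at the first time of use and available at the second. The R² and the calibration plot of that fit describe a model usable after surgery.

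The size can be given only as a count: 1 of 12 Study I candidates, in 1 of 3 planned models. How much R² would change without this variable depends on data that the SAP does not report.

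**The case against.** The strongest reply is that the conflict is with one phrase in the background. The SAP says only that the model could be applied in practice, does not name which of the three models is meant, and gives a second use that works well with a postoperative film. The objectives set no time of prediction. Fracture zone length also describes the injury, so the obstacle is how it was measured here, and the variable may not survive data reduction. All of this stands, and it is why the point is minor. It does not remove the mismatch between a stated use and the definition of an input, and nothing elsewhere in the SAP resolves it.

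Three stronger readings are tempting, and the SAP does not support them.

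- **Other predictors may also be postoperative.** The classification ("Distal femur fractures were classified according to the AO/OTA classification system 2007"), the segmental comminution derived from it ("Segmentally comminuted fractures were defined as A3, C2 and C3- fractures according to the AO/OTA-classification") and medial comminution ("more than one fracture line reached the medial cortex on the antero-posterior x-ray") are given without a statement of when the film was taken. A reader might infer that these were read after surgery too. That would rest on silence alone. The text says postoperative for fracture zone length only, and detail on film reading may stand in a protocol that is not at hand.
- **A definite number of preoperative predictors.** A reader might try to state how many terms a preoperative model would hold. Table 2 lists candidates. The number of fitted terms depends on the reduction step, and segmental comminution overlaps with AO/OTA class by definition.
- **A claim of preoperative accuracy.** Statistical principles uses R² to interpret what it calls baseline predictors. A reader might take that to mean preoperative. The sentence covers all fitted models, including the two with plate and screw variables, so it cannot carry that meaning.

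**Conclusion.** The point holds in a limited form and is minor. If fracture zone length is retained, the Study I model cannot be applied as defined before surgery, although the background names that use. No planned estimate becomes wrong, the accuracy objective can be met as written, and the follow-up use is unaffected.

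The conclusion rests on two conditions. The variable must survive data reduction, which the SAP leaves open. Study I must be the model meant for use before surgery, which follows from its being the only one without treatment-related variables but is not stated. The effect on model performance is unknown.

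**What to change.** Add to Statistical principles that Study I will also be fitted without fracture zone length, on the same imputed datasets, with its own R² and calibration plot. Base any statement about use before surgery on that version only. Present the version with fracture zone length as applicable after surgery, for planning follow-up.

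If the extra model is not fitted, remove the preoperative use from the background and keep the follow-up use.

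The first option costs one more fit on data already collected and a sentence or two in the SAP. Its downside is one more model to report and possibly a slightly lower R². The second needs no modelling but gives up the preoperative use.
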